6.5.4 Erythematous Rash With or Without Pruritus

As with bortezomib, rash with or without pruritus has been reported with ixazomib, primarily at the higher doses tested and when given with agents where rash is an overlapping toxicity. The rash may range from limited erythematous areas, macular and/or small papular bumps that may or may not be pruritic over a few areas of the body, to a more generalized eruption that is predominately on the trunk or extremities. Rash has been most commonly characterized as maculopapular or macular. To date, when it does occur, rash is most commonly reported within the first 3 cycles of therapy. The rash is often transient, self-limiting, and is typically Grade 1 to 2 in severity.

Symptomatic measures such as antihistamines or corticosteroids (oral or topical) have been successfully used to manage rash and have been used prophylactically in subsequent cycles. The use of a topical, IV, or oral steroid (eg, prednisone \leq 10 mg per day or equivalent) is permitted. Management of a Grade 3 rash may require intravenous antihistamines or corticosteroids. Administration of ixazomib (and/or other causative agent if given in combination) should be modified per protocol and re-initiated at a reduced level from where rash was noted (also, per protocol).

In line with clinical practice, dermatology consult and biopsy of Grade 3 or higher rash or any SAE involving rash is recommended. Prophylactic measures should also be considered if a patient has previously developed a rash (eg, using a thick, alcohol-free emollient cream on dry areas of the body or oral or topical antihistamines). A rare risk is Stevens-Johnson Syndrome, a severe and potentially life-threatening rash with skin peeling and mouth sores, which should be managed symptomatically according to standard medical practice. Punch biopsies for histopathological analysis are encouraged at the discretion of the investigator.

6.5.5 Thrombocytopenia

Blood counts should be monitored regularly as outlined in the protocol with additional testing obtained according to standard clinical practice. Thrombocytopenia may be severe but has been manageable with platelet transfusions according to standard clinical practice. Ixazomib administration should be modified as noted as per dose modification recommendations in the protocol when thrombocytopenia occurs (see Table 6-2). Therapy can be reinitiated at a reduced level upon recovery of platelet counts. A rare risk is thrombotic thrombocytopenic purpura (TTP), a rare blood disorder where blood clots form in small blood vessels throughout the body characterized by thrombocytopenia, petechiae, fever, or possibly more serious signs and symptoms. TTP should be managed symptomatically according to standard medical practice.

6.5.6 Neutropenia

Blood counts should be monitored regularly as outlined in the protocol with additional testing obtained according to standard clinical practice. Neutropenia may be severe but has been manageable. Growth factor support is not required but may be considered according to standard clinical practice. Ixazomib administration should be modified as noted as per dose modification recommendations in the protocol when neutropenia occurs (see Table 6-2). Therapy can be reinitiated at a reduced level upon recovery of ANCs.

6.5.7 Fluid Deficit

Dehydration should be avoided since ixazomib may cause vomiting, diarrhea, and dehydration. Acute renal failure has been reported in patients treated with ixazomib, commonly in the setting of the previously noted gastrointestinal toxicities and dehydration.

Fluid deficit should be corrected before initiation of study drug and as needed during treatment to avoid dehydration.

6.5.8 Hypotension

Symptomatic hypotension and orthostatic hypotension with or without syncope have been reported with ixazomib. Blood pressure should be closely monitored while the patient is on study treatment and fluid deficit should be corrected as needed, especially in the setting of concomitant symptoms such as nausea, vomiting, diarrhea, or anorexia. Patients taking medications and/or diuretics to manage their blood pressure (for either hypo- or hypertension) should be managed according to standard clinical practice, including considerations for dose adjustments of their concomitant medications during the course of the trial. Fluid deficit should be corrected before initiation of study drug and as needed during treatment to avoid dehydration.

6.5.9 Posterior Reversible Encephalopathy Syndrome

One case of posterior reversible encephalopathy syndrome, which ultimately resolved, has been reported with ixazomib. This condition is characterized by headache, seizures and visual loss, as well as abrupt increase in blood pressure. Diagnosis may be confirmed by magnetic resonance imaging (MRI). If the syndrome is diagnosed or suspected, symptom-directed treatment should be maintained until the condition is reversed by control of hypertension or other instigating factors.

6.5.10 Transverse Myelitis

Transverse myelitis has also been reported with ixazomib. It is not known if ixazomib causes transverse myelitis; however, because it happened to a patient receiving ixazomib, the possibility that ixazomib may have contributed to transverse myelitis cannot be excluded.

7.0 PHARMACEUTICAL INFORMATION

7.1 Ixazomib

7.1.1 Description

Ixazomib will be provided by the study in strengths of 4.0, 3.0, and 2.3 mg capsules as the active boronic acid. The different dose strengths are differentiated by both capsule size and color as described below:

Dose Strength	Capsule Size	Capsule Color
4.0 mg	Size 4	Ivory
3.0 mg	Size 3	Light gray
2.3 mg	Size 2	Light pink

For additional details, please see Section 1.2 or refer to the ixazomib IB.

7.1.2 Storage, Handling, and Accountability

Upon receipt at the investigative site, ixazomib should remain in the blister and carton provided until use or until drug is dispensed. Ensure that the drug is used before the retest expiry date provided by Millennium. Expiry extensions will be communicated accordingly with updated documentation to support the extended shelf life.

In countries where local regulations permit, ixazomib capsules dispensed to the patient for take-home dosing should remain in the blister packaging until the point of use. The investigative site is responsible for providing the medication to the patient in the correct daily dose configurations. Comprehensive instructions should be provided to the patient in order to ensure compliance with dosing procedures. Patients should be instructed to return their empty blister packs to the investigative site, rather than discarding them. Reconciliation will occur accordingly when the patient returns for their next cycle of take-home medication.

The ixazomib capsules should be stored according to the label. When applicable, the container should be stored at the investigative site refrigerated (36°F to 46°F, 2°C to 8°C) and patients should be instructed to store the medication refrigerated (36°F to 46°F, 2°C to 8°C) for the duration of each cycle. Any extreme in temperature should be reported as an excursion and should be dealt with on a case-by-case basis.

Because ixazomib is an investigational agent, it should be handled with due care. Patients should be instructed not to chew, break, or open capsules. In case of contact with broken capsules, raising dust should be avoided during the clean-up operation. The product may be harmful by inhalation, ingestion, or skin absorption. Gloves and protective clothing should be worn during cleanup and return of broken capsules and powder to minimize skin contact.

The area should be ventilated and the site washed with soap and water after material pick-up is complete. The material should be disposed of as hazardous medical waste in compliance with federal, state, and local regulations.

In case of contact with the powder (eg, from a broken capsule), skin should be washed immediately with soap and copious amounts of water for at least 15 minutes. In case of contact with the eyes, copious amounts of water should be used to flush the eyes for at least 15 minutes. Medical personnel should be notified. Patients are to be instructed on proper storage, accountability, and administration of ixazomib, including that ixazomib is to be taken as intact capsules.

7.1.3 Packaging and Labeling

Ixazomib will be labeled and handled as open-label material, and packaging labels will fulfill all requirements specified by governing regulations.

The capsules are individually packaged using cold-form foil-foil blisters that are in a child-resistant carton. There are 3 capsules in each wallet/carton.

7.1.4 Destruction

Investigational ixazomib (expired or end of study) should be destroyed on site according to the institution's standard operating procedure. Be sure to document removal and destruction on drug accountability logs.

7.1.5 Compliance

Study drug will be administered or dispensed only to eligible patients under the supervision of the investigator or identified sub-investigator(s). The appropriate study personnel will maintain records of study drug receipt and dispensing.

7.2 Lenalidomide

7.2.1 Lenalidomide Description

Lenalidomide will not be provided by the study. It will be sourced from each patient's commercial pharmacy of choice in accordance with the Celgene Corporation's Revlimid REMS® program.

7.3 Dexamethasone

7.3.1 Description

Dexamethasone will not be provided by the study. It will be sourced from each patient's commercial pharmacy of choice.

8.0 STUDY CALENDAR

Please note that all assessments allow a window of +/-3 days for scheduling issues.

	Screening		Consolidation ³			Restaging ⁴	Maintenance ⁵			EOS ⁷	F/U ⁸
	Prior to ASCT ¹	Prior to beginning consolidation ²	D1	D8	D15		D1	D8	D15		
Informed consent	X										
H&P, ECOG PS, plasmacytoma assessment	X	X	X ¹³			X	X ^{13,14}			X	X ¹⁵
CBC & CMP	X		X ¹³		X ⁶	X	X ^{13,14}			X	
SPEP and immunofixation	X	X	X ¹³			X	X ^{13,14}			X	
24h urine for total protein, UPEP, and immunofixation ⁹	X	X	X ¹³			X	X ^{13,14}			X	
Serum-free light chains & β2 microglobulin	X	X	X ¹³			X	X ^{13,14}			X	
Quantitative immunoglobulins (IgA, IgG, IgM)	X	X	X ¹³			X	X ^{13,14}			X	
Serum βhCG ¹⁰	X	X	X				X			X	
Bone marrow biopsy and aspirate ¹¹	X	X				X	X ¹⁶				
Central labs ¹² (MRD Analysis)		X				X	X ¹⁶				
Central labs ¹² (Hevylite)	X		X ¹³			X	X ^{13,14}			X	
Central labs ¹⁸ (Sub-study)		X ¹⁸					X ¹⁸				
Ixazomib			X	X	X		X	X	X		
Lenalidomide			Days 1-21				Days 1-28				
Dexamethasone			X	X	X						
Administration Questionnaire ¹⁷			X				X				
Adverse events assessment			X ----- X								

1. Day -60 to Day -2

2. Day +80 to Day +120; to occur within 28 days prior to C1D1 of consolidation

3. 4 28-day cycles

4. Prior to beginning maintenance (approx. Day +192 to Day +232); to occur within 28 days after completing C4 of consolidation and within 28 days prior to C1D1 of maintenance

5. 28-day cycles; continued until progression or unacceptable toxicity

6. Cycles 1-2 only

7. Within 30 days of last dose of study drug(s)

8. Every 3 months for 18 months

9. Repeat 24h urine only required for patients with ≥ 200 mg/24h of M-protein at screening

10. Women of childbearing potential only; 2 negative tests are required within 14 days before study drug dosing on C1D1 of consolidation

11. Bone marrow aspirate and core biopsy – differential required; Cytogenetics, and fluorescent *in situ* hybridization (FISH) studies performed per institutional guidelines.

12. See Section 9.0

13. Not required on C1D1 if screening/restaging visit occurred within 28 days prior

14. C1-C4 then every 3 cycles thereafter (i.e., C7, C10, C13 ...)

15. A telephone call to assess OS and PFS can be made in lieu of a physical exam

16. Cycle 13 for all patients. Cycle 25 and 37 also required for patients in suspected or confirmed CR/sCR at that time.

17. See Appendix D. Patient to complete following each cycle of study treatment (consolidation and maintenance).
18. Only performed on selected patients at Washington University or Ohio State University. See Appendix F.

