A woman of childbearing potential is defined as a sexually mature woman who: 1) has not undergone a hysterectomy or bilateral oophorectomy or 2) has not been naturally postmenopausal for at least 24 consecutive months. Women of childbearing potential are required to have a negative serum or urine pregnancy test within 10-14 days prior to and again no more than 24 hours before the first dose of lenalidomide. Women of childbearing potential are required to use two forms of contraception at the same time, including one highly effective method (i.e., intrauterine device, hormonal (birth control pills, injections, or implants), tubal ligation, partner's vasectomy) and one additional effective (barrier) method (i.e., latex condom, diaphragm, cervical cap), from the time of signing of the informed consent form through 90 days after the last dose of study drug. Male patients engaged in a sexual relationship with a woman of childbearing potential must agree to use a latex condom during sexual contact, even if he has had a successful vasectomy.

If a patient is suspected to be pregnant, both study drugs should be immediately discontinued. In addition a positive urine test must be confirmed by a serum pregnancy test. If it is confirmed that the patient is not pregnant, the patient may resume dosing.

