6.2 Criteria for Beginning a New Treatment Cycle

For a new cycle of treatment to begin, the patient must meet the following criteria:

- ANC must be $\geq 1,000/\text{mm}^3$.
- Platelet count must be $\geq 75,000/\text{mm}^3$.
- All other treatment related non-hematologic toxicity (except for alopecia) must have resolved to \leq Grade 1 or to the patient's baseline condition

If the patient fails to meet the above-cited criteria for initiation of the next cycle of treatment, dosing should be delayed for 1 week. At the end of that time, the patient should be re-evaluated to determine whether the criteria have been met. If the criteria have been met, resume at previous dose levels.

If the patient continues to fail to meet the above-cited criteria, delay therapy and continue to re-evaluate weekly. If a delay of > 2 weeks is required, reduce the suspected drug(s) by one dose level when treatment is resumed. Dosing adjustments should not occur in both ixazomib and lenalidomide simultaneously.

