APPENDIX F: Correlative Sub-study

Up to 50 patients (approximately 20 in each maintenance arm) will provide informed consent to the optional correlative sub-study to study the effect of ixazomib maintenance on the immune system.

Approximately 20 ml of peripheral blood in EDTA (pink top) tube(s) will be collected at the following time points:

- Prior to beginning consolidation therapy
- Cycle 1 Day 1 of maintenance (pre-drug)
- Cycle 4 Day 1 of maintenance (pre-drug)

Instructions for handling and shipment of samples will be provided in the study lab binder. Lymphocyte phenotyping and functional assays will be performed at the conclusion of the correlative sub-study.

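### Calendar note 10 and the blanket ±3-day window allow pregnancy-test timing that Section 5.6 does not, and the window has no exception for the Day 1 counts that gate a cycle

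*Combined protocol and SAP*

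**What the plan says.** Three parts of the protocol set the timing of assessments that must come before a dose.

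- **Section 8.0, calendar header:** "Please note that all assessments allow a window of +/-3 days for scheduling issues". No exception is stated.
- **Section 8.0, note 10** (serum hCG row, women of childbearing potential): "2 negative tests are required within 14 days before study drug dosing on C1D1 of consolidation". It sets no spacing between the two tests, no 24-hour limit, and no reference to Section 5.6. The row also has its own Day 1 mark in consolidation.
- **Section 5.6:** the same women need a "negative serum or urine pregnancy test within 10-14 days prior to and again no more than 24 hours before the first dose of lenalidomide".
- **Section 6.2**, which lists neutrophil, platelet and toxicity criteria: "For a new cycle of treatment to begin, the patient must meet the following criteria". If they are not met: "If the patient fails to meet the above-cited criteria for initiation of the next cycle of treatment, dosing should be delayed for 1 week". No maximum age for the counts is given.

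**The concern.** Sites schedule visits from the calendar. If the calendar is looser than the section it summarises, a site can follow it exactly and still depart from the protocol.

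For the pregnancy tests, a woman could start lenalidomide with her last negative test well outside the 24 hours that Section 5.6 requires. That section gives the teratogenic risk as the reason for the testing, so this is a participant-safety matter, and it also determines what counts as a protocol deviation.

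For the blood counts, Section 6.2 works only if the result is known before the cycle's first dose. A calendar that accepts the Day 1 count after that dose gives the site two incompatible messages.

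**Working it through.** No sample size or power figure is involved. The check sets the texts side by side and does simple timing arithmetic.

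**1. Do note 10 and Section 5.6 concern the same dose?** Note 10 refers to dosing on Cycle 1 Day 1 of consolidation. Lenalidomide is given on Days 1-21 of each consolidation cycle (Section 5.2.2), so its first on-study dose is that same day. The two rules govern the same event and should agree.

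**2. Note 10 alone.** Take tests 13 and 12 days before the dose.
- Note 10: both are within 14 days, so it is satisfied.
- Section 5.6, first test: 13 lies between 10 and 14, so it is satisfied.
- Section 5.6, second test: the later test is 12 days before the dose, or 12 × 24 = 288 hours, against a limit of 24. It is not satisfied.

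**3. Note 10, the Day 1 mark and the window together.** Because the hCG row has its own Day 1 entry, note 10 should not be read in isolation. Take one test 12 days before the dose, and draw the Day 1 test three days early.
- Note 10: 12 and 3 are both within 14, so it is satisfied.
- Calendar Day 1 entry: three days early is inside ±3 days, so it is satisfied.
- Section 5.6, first test: 12 lies between 10 and 14, so it is satisfied.
- Section 5.6, second test: 3 × 24 = 72 hours against 24, which is 72 − 24 = 48 hours too early. It is not satisfied.

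So a schedule that meets every calendar entry for the test can still miss Section 5.6, and the early side of the window is the cause.

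**4. Day 1 counts and Section 6.2.** The two sides of the window behave differently.
- Early side (up to three days before Day 1): no conflict, because Section 6.2 sets no limit on how old a count may be.
- Late side: Day 1 + 3 = Day 4. In consolidation, by then the Day 1 ixazomib dose (one of the cycle's three) and the lenalidomide doses of Days 1-3, possibly Day 4 as well, would have been taken. Section 6.2 responds to a failed criterion by delaying the dose, so a count obtained after the dose cannot do that job.

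At Cycle 1 Day 1 a separate footnote to the counts row applies ("Not required on C1D1 if screening/restaging visit occurred within 28 days prior"), so this step matters mainly for later cycles that have a scheduled Day 1 count.

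**The case against.** The best defence is that the protocol must be read as a whole. Note 10 and Section 5.6 can be met together, for example with one test 12 days before the dose and one in the last 24 hours, so note 10 is a loose summary and does not force a breach. Inclusion criteria 7 and 9 require compliance with the Revlimid REMS program, and lenalidomide is supplied only under it. For the counts, Section 6.2 itself bars starting a cycle until its criteria are met. The window could be read as moving the whole visit, dosing included. Drug is prescribed one cycle at a time in consolidation and in maintenance Cycles 1-3, which makes a patient who doses on Day 1 and returns for counts on Day 4 an unlikely case.

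Much of this stands, and it lowers the practical risk. It does not make the passages agree. Being able to satisfy both rules does not help a site that reads only the looser one. The protocol does not reproduce the REMS test timing in the calendar. The header speaks of assessments and does not tie the dose to them. For the counts, the defence reduces the point to a missing exception, which is why it is secondary.

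Several stronger readings might be inferred, and the documents do not support them:
- *Counts taken before Day 1 contradict Section 6.2.* They do not, since that section sets no lookback limit.
- *A pregnancy test after the dose may count.* Note 10 and Section 5.6 both require the tests to precede it.
- *The window lets the baseline MRD marrow or the Appendix F immune samples be taken after dosing.* Calendar note 2, Sections 9.1 and 9.2, and Appendix F each fix those samples as pre-treatment or pre-drug, and a general scheduling allowance does not override that.
- *The harm can be sized by adding the window to note 10's limit, or by counting all cycle starts.* Note 10 states its own 14-day limit, and a count of cycle starts says nothing about how often a dose would precede its count.

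**Conclusion.** The concern holds in two parts of unequal weight. The main part is a direct inconsistency: note 10 and the early side of the ±3-day window each accept a last pre-dose pregnancy test outside the 24 hours in Section 5.6, 12 days before the dose in one example and 72 hours in the other. It is limited to women of childbearing potential. The documents give no estimate of their number, so no count of affected patients is offered.

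The secondary part is an omission: the header has no exception for the Day 1 neutrophil and platelet counts, so a literal reading puts a count as late as Day 4 on schedule. Section 6.2 still forbids starting the cycle without meeting its criteria, so this is conflicting guidance and not permission to skip the gate.

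Both parts rest on reading the header as written, with the window applying to the assessment and not to the dose. The note 10 example does not depend on that reading. No endpoint, sample size, power or error rate is affected. The change is still worth making, because the point concerns safety and is nearly free to correct.

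**What to change.** 1. Reconcile note 10 with Section 5.6 so that both give one identical timing for the two pregnancy tests. Which timing applies is for the clinical team to decide.
2. Add a sentence to the calendar header: the ±3-day window neither widens a timing limit set in another section nor moves a gating assessment past the dose it gates. Both halves are needed. Barring movement past the dose would deal with the Day 1 counts but leave the 72-hour pregnancy test open.

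The cost is slightly less scheduling flexibility around Day 1. Note 10 and Section 5.6 both already ask for two tests, so aligning their timing adds none.

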3.0 PATIENT SELECTION

3.1 Inclusion Criteria

Each patient must meet all of the following inclusion criteria to begin IRD Consolidation

1. Between the ages of 18 and 70 years of age (inclusive) at time of enrollment
2. Voluntary written consent must be given before performance of any study-related procedure not part of standard medical care, with the understanding that consent may be withdrawn by the patient at any time without prejudice to future medical care.
3. Histologically confirmed diagnosis of symptomatic multiple myeloma. (Patients with multiple myeloma with secondary amyloidosis are eligible.)
4. Received at least two cycles of any regimen as initial systemic therapy for multiple myeloma and are within 2-16 months of the first dose of initial therapy
5. Eastern Cooperative Oncology Group (ECOG) performance status and/or other performance status 0, 1, or 2 (see Appendix A).
6. Adequate organ function as defined below:
 - Absolute neutrophil count (ANC) $\geq 1,000/\text{mm}^3$.
 - Platelet count $\geq 75,000/\text{mm}^3$; platelet transfusions to help patients meet eligibility criteria are not allowed within 7 days before study enrollment.
 - Total bilirubin $\leq 1.5 \times$ the upper limit of the normal range (ULN).
 - Alanine aminotransferase (ALT) and aspartate aminotransferase (AST) $\leq 3 \times$ ULN.
 - Calculated creatinine clearance ≥ 30 mL/min (see Appendix B).
7. Women of childbearing potential (as defined in Section 5.6) must follow pregnancy testing requirements as outlined in the Revlimid REMS® program material. This is defined as either committing to continued abstinence from heterosexual intercourse or beginning TWO acceptable methods of contraception (one highly effective method and one additional effective method (as defined in Section 5.6) AT THE SAME TIME) at least 28 days prior to the start of lenalidomide, for the duration of study participation, and for 28 days following the last dose of lenalidomide. Women of childbearing potential must also agree to ongoing pregnancy testing.
8. Men must agree to use a latex condom during sexual contact with a woman of childbearing potential even if they have had a successful vasectomy. All patients must be counseled at a minimum of every 28 days about pregnancy precautions and risks of fetal exposure. Should a woman become pregnant or suspect she is pregnant while participating in this study, she must inform her treating physician immediately.

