9.0 CENTRAL LABS

9.1 Mayo Clinic MFC MRD Panel

Approximately 5 ml of bone marrow aspirate in EDTA (pink top) tube(s) will be collected at the following time points:

- Prior to beginning consolidation therapy
- Prior to beginning maintenance therapy
- Cycle 13 Day 1 of maintenance therapy
- Cycle 25 Day 1 of maintenance therapy*
- Cycle 37 Day 1 of maintenance therapy*

*- Only required for patients in suspected or confirmed CR/sCR at that time

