12.1.1 Stringent Complete Response

Stringent complete response (sCR) requires all of the following:

- CR as defined below
- Normal free light chain ratio (0.26-1.65)
- Absence of clonal cells in the bone marrow by immunohistochemistry or immunofluorescence

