12.1.2 Complete Response

Complete response (CR) requires all of the following:

- Disappearance of monoclonal protein by both protein electrophoresis and immunofixation studies from the blood and urine
- If serum and urine monoclonal protein are unmeasurable, Normal free light chain ratio (0.26-1.65)
- <5% plasma cells in the bone marrow
- Disappearance of soft tissue plasmacytoma

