12.1.3 Very Good Partial Response

Very good partial response (VGPR) requires all of the following:

- Serum and urine monoclonal protein detectable by immunofixation but not on electrophoresis
OR
 $\geq 90\%$ reduction in serum monoclonal protein with urine monoclonal protein < 100 mg per 24 hours
- If serum and urine monoclonal protein are unmeasurable, a $\geq 90\%$ decrease in difference between the involved and uninvolved free light chain levels is required in place of monoclonal protein criteria (The absolute decrease must be > 10 mg/dl)
- If present, > 50% reduction in the size of soft tissue plasmacytomas (by clinical or radiographic examinations)

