12.1.6 Progressive Disease or Clinical Relapse

Progressive disease (PD) requires one or more of the following:

- $\geq 25\%$ increase in the level of serum monoclonal protein, which must also be an absolute increase of at least 0.5 g/dL and confirmed on a repeat investigation
- $\geq 25\%$ increase in 24-hour urine monoclonal protein, which must also be an absolute increase of at least 200 mg/24hr and confirmed on a repeat investigation.
- If serum and urine monoclonal protein are unmeasurable, $\geq 25\%$ increase in the difference between involved and uninvolved free light chain levels, which must also be an absolute increase of at least 10 mg/dL and confirmed on a repeat investigation
- $\geq 25\%$ increase in plasma cells in a bone marrow aspirate or on trephine biopsy, which must also be an absolute increase of at least 10%.
- Definite increase in the size of existing lytic bone lesions or soft tissue plasmacytomas. A definite increase is defined as at least 50% (and at least 1 cm) increase as measured serially as the sum of the products of the cross-diameters of the lesions.
- Development of new bone lesions or soft tissue plasmacytomas (not including compression fracture).
- Development of hypercalcaemia (corrected serum calcium > 11.5 mg/dL or 2.8 mmol/L not attributable to any cause other than progressive multiple myeloma).
- Decrease in hemoglobin > 2 g/dl not attributable to any cause other than progressive multiple myeloma
- Increase in creatinine by > 2 mg/dl not attributable to any cause other than progressive multiple myeloma
- Other worsening laboratory result, or clinical condition that the treating physician determines is not attributable to any cause other than progressive multiple myeloma

Note: A response of progressive disease/clinical relapse nullifies any other concurrent response. For example, at a given time point a participant meets criteria for VGPR but has development of new bone lesions the response is PD not VGPR.

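### Calendar note 9 waives the repeat urine tests that section 12.1 needs for CR and sCR in patients with detectable urine M-protein below 200 mg/24h at screening

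*Combined protocol and SAP*

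**What the plan says.** The calendar row at issue is "24h urine for total protein, UPEP, and immunofixation". It is marked at both screening visits (before ASCT and before consolidation), on Day 1 of consolidation cycles, at restaging, on Day 1 of maintenance cycles and at end of study. Note 9 qualifies the row: "Repeat 24h urine only required for patients with ≥ 200 mg/24h of M-protein at screening".

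Section 12.1 carries no matching exemption:

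- CR (12.1.2) requires "Disappearance of monoclonal protein by both protein electrophoresis and immunofixation studies from the blood and urine".
- sCR (12.1.1) requires "CR as defined below", so it inherits the urine condition.
- VGPR (12.1.3) has two M-protein routes, and both use urine. One is disease visible on immunofixation but not on electrophoresis. The other is a 90% or greater "reduction in serum monoclonal protein with urine monoclonal protein < 100 mg per 24 hours". Free light chains replace these only when serum and urine M-protein are both unmeasurable.
- Progression (12.1.6) includes a 25% or greater "increase in 24-hour urine monoclonal protein, which must also be an absolute increase of at least 200 mg/24hr", confirmed on repeat. It is one of several sufficient criteria.
- Relapse from CR (12.1.7) can be declared on paraprotein returning in urine alone.

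Section 15.3 plans CR and overall response rates with 95% confidence intervals after consolidation, and compares response and PFS between the maintenance arms.

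**The concern.** A site that follows the calendar exactly may hold no urine result after screening for an exempt patient, yet it must make response calls whose definitions need one. Neither section 12.1 nor section 15.3 says how to score a missing urine result or whether a screening result carries forward. One site could call CR on serum and marrow alone, and another could decline to call it. Both would be within the protocol, and the CR rate would then depend partly on local habit in an open-label, multicenter trial.

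The gap is wider because screening is not an untreated baseline. Section 3.1 asks for patients who have "Received at least two cycles of any regimen as initial systemic therapy for multiple myeloma", so someone with substantial urine disease at diagnosis can fall under 200 mg/24h by screening and lose urine follow-up. Section 5.1 also lets patients who consent after ASCT omit pre-ASCT assessments not done as standard care. Their only screening urine may then be post-transplant.

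**Working it through.** No sample size, power or event count depends on this point, so there is no figure in the plan to reproduce. The check sets note 9 against each definition. Let U be urine M-protein at screening, in mg/24h, with U < 200, so that no repeat urine is required.

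| Call | What 12.1 needs from urine | Available from required tests when U < 200 |
|---|---|---|
| CR, sCR | Negative electrophoresis and immunofixation | Nothing after screening |
| VGPR, serum measurable, U of 100-199 | A value below 100, or positivity on immunofixation only | Screening value fails the limit of 100; no later value required |
| VGPR, serum measurable, U < 100 | Same | Limit met only by carrying the screening value forward, which the plan does not state |
| VGPR, serum and urine both unmeasurable | None; free light chains are used | Derivable: free light chains are scheduled for everyone |
| PR | 90% reduction, or a value below 200 | Screening value is already below 200 |
| PD, urine criterion | Rise of at least 25% and at least 200 | Not observable without repeat urine |
| PD, other criteria | None | Not affected by note 9 |
| Relapse from CR, urinary | Reappearance in urine | Not observable without repeat urine |

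**CR.** The free light chain line in 12.1.2 does not fill the gap. It applies only when serum and urine are both unmeasurable, and it stands in a list of which every item must be met. It adds a condition and does not replace urine immunofixation.

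**Threshold.** The exemption limit of 200 mg/24h equals the PR urine limit in 12.1.4. It is looser than the VGPR limit of 100 and the CR requirement of no detectable protein.

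**Urine progression.** Section 12.1.6 states no reference value, so the screening value is used here as an assumption. For U < 200, 25% of U is below 50 mg, so the absolute rise of 200 governs. The qualifying value is U + 200: 200 at U = 0, 300 at U = 100 and 399 at U = 199. None of these would be seen unless urine were collected again.

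**Which screening urine.** Both screening columns carry the urine test, and note 9 does not say which one sets the threshold. If both count as screening, every patient has a urine result at Day +80 to +120. A negative immunofixation there gives some basis for a later CR. If the pre-ASCT value alone sets the threshold, the pre-consolidation sample could itself be read as a waived repeat.

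**Size per patient.** With 220 evaluable patients, one CR call adds 1/220 = 0.45 percentage points to the consolidation CR rate. With 110 per maintenance arm, one call adds 1/110 = 0.91 points.

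**The case against.** Much of the case on the other side stands.

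- Note 9 removes a requirement and does not prohibit the test, so sites may collect urine to confirm CR or suspected progression. That is true, but it leaves ascertainment to discretion.
- A pre-consolidation urine may exist for every patient. This rescues those already negative by then. It does not help those still positive.
- A reader might infer that CR, VGPR and progression are all underivable for every patient below 200 mg/24h. The documents do not support that. VGPR has its free light chain route, and progression can be declared on serum, marrow, bone, laboratory or clinical grounds.
- A reader might infer that MRD testing at cycles 25 and 37 is blocked. It is not: sections 9.1 and 9.2 mark those samples "Only required for patients in suspected or confirmed CR/sCR at that time", and a suspected CR needs no urine result.
- The primary analysis is the change in MRD-negative rate and uses no urine. Section 15.1 describes the maintenance comparison as pilot data, and note 9 applies equally to both arms.
- Section 12.1 refers to the IMWG criteria, which cannot be consulted here. They may address patients with little urine protein, but the definitions written into the protocol do not.

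None of this supplies the urine result that the protocol's own CR definition requires after consolidation or in maintenance.

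**Conclusion.** The conflict is real and concerns secondary endpoints. For patients with detectable urine M-protein below 200 mg/24h at screening, CR and sCR after consolidation or in maintenance cannot be supported from required assessments unless urine was already negative before consolidation. At 100-199 mg/24h, VGPR by the M-protein route has the same problem. Urine-only progression and urinary relapse from CR can be missed or found late, which would lengthen PFS for those patients.

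The total effect cannot be stated. The documents give neither the distribution of screening urine protein nor the share of patients who would remain urine-positive once serum and marrow had cleared. A bias of several points in the CR rate is possible but has no anchor in the plan. An unconfirmed CR call is also not necessarily a wrong one.

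**What to change.** Reconcile note 9 with section 12.1:

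1. Limit the exemption to routine cycle-by-cycle collections. Whatever the screening value, require urine electrophoresis and immunofixation at restaging, when CR or sCR is first suspected in maintenance, and when progression or relapse is being assessed.
2. State in note 9 which of the two screening visits sets the 200 mg/24h threshold, and whether the pre-consolidation urine is required of everyone.
3. In section 15.3, report the CR rate twice where urine results are absent: once with all CR calls and once with urine-confirmed CR only. State in advance whether a negative pre-consolidation urine counts as confirmation.

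An automatic downgrade to VGPR when urine is missing is not a sound substitute. It would take CR away from exempt patients who never had urine disease, and it would give VGPR to patients at 100-199 mg/24h who have no value showing that they meet the limit of 100.

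The cost is an edit to one calendar note, a few lines in sections 12.1 and 15.3, and a few extra urine collections in patients who are now exempt. The test is already in the calendar.
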